#### **4.5.5 Subgroup Analyses**

For the sub-group analysis the MMRM for change from baseline in BCVA will be used in the following subgroups:

- Gender

- CNV lesion type at baseline (FACNV) CNV on FA as Classic, Classic+occult or Occult
- CNV lesion type by ICG at baseline as 3 categories: PCV, RAP or Neither
- OCT analysis: Fluid Type at baseline (by type of fluid – intraretinal, subretinal or other)
- BCVA Categories at baseline (20/40 or better vs worse than 20/40, 20/200 or better vs worse than 20/200),
- Baseline LLD quartiles or medians.

The subgroup analyses will be performed separately for each sub-group factor in populations A and C. For population C the subgroups will be defined based on the baseline defined for this population. Subgroup analyses in population C will be performed only if there are a sufficient number of patients in this population.

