6. STATISTICAL CONSIDERATIONS AND ANALYSIS PLAN

6.1 DETERMINATION OF SAMPLE SIZE

6.1.1 Sample Size and Power for Treatment-Naive Population Evaluation

The sample size for the treatment-naive population is based on the primary efficacy outcome of mean change in BCVA from baseline to Week 36. Each RO6867461 dose

or dose regimen group (Arms B, C, and D) will be compared to the control group (Arm A).

Consider 68 patients randomized to Arm A and 45 randomized to each of Arms B, C, and D, with a drop-out rate of 10%. Assuming a standard deviation of 13.5 letters, this sample size would provide approximately 80% power to detect a true difference of 5.9 letters at the one-sided α level of 10%. The minimum detectable difference would be approximately 3.5 letters.

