#### **4.5.1 Primary Efficacy Endpoint**

##### **4.5.1.1 Evaluation in the Treatment-Naïve Population**

For the evaluation of efficacy in the treatment-naïve population, all patients in Population A will be used.

The primary efficacy variable is the BCVA change from baseline to Week 36. The primary efficacy analysis will be performed using a Mixed Model for Repeated Measurement (MMRM) model. The model will include the categorical covariates of randomization stratification indicator for presence of RAP or PCV, treatment group, visit, and visit by treatment group interaction and the continuous covariate of baseline BCVA. An unstructured variance-covariance model will be used to account for within-patient correlation, but another variance-covariance structure, such as AR(1), may be used in case of convergence issues.

In case of a significant departure from the normality assumptions required for the MMRM, a nonparametric Mann-Whitney  $U$  test will be used to compare change from baseline between treatment arms at given visits.

The primary statistical tests will test the null hypotheses:

$H_0$ : no difference between each of the treatment group (Arms B, C, or D) and the control group (Arm A), in mean BCVA change from baseline to Week 36 vs.

$H_A$ : Arms B, C or D means are different from Arm A mean.

The model-based estimate of the difference between each of the treatment group (Arms B, C, and D) and the control group (Arm A) at Week 36, together with 95% confidence intervals and corresponding p-value will be reported as the primary efficacy measures in this population.

The mean and 95% confidence interval (CI) within each treatment group and for the difference in change from baseline between RO6867461 treatment groups (Arms B, C, and D) and the control group (Arm A) at the other time-points will also be reported. There will be no formal correction for multiple comparisons.

For the primary endpoints, a statistically significant difference at week 36 between any of the treatment Arms B, C, or D and Arm A will be concluded if the corresponding unadjusted 2-sided p-value is below 0.2.

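### SAP 4.5.5 fits the MMRM within each subgroup level and plans no treatment-by-subgroup estimate or test, so it does not directly assess whether the effect differs between subgroups

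*SAP*

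**What the plan says.** SAP 4.5.5 sets the subgroup method in one sentence: "For the sub-group analysis the MMRM for change from baseline in BCVA will be used in the following subgroups". The factors are gender, lesion type on FA, lesion type on ICG (PCV, RAP or neither), fluid type, BCVA category (one split at 20/40 and one at 20/200) and low-luminance deficit in quartiles or at the median. It adds: "The subgroup analyses will be performed separately for each sub-group factor in populations A and C". Population C subgroups are defined at that population's own baseline, which SAP 4.4.2 sets at Week 12.

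The model is that of SAP 4.5.1.1. It has the "categorical covariates of randomization stratification indicator for presence of RAP or PCV, treatment group, visit, and visit by treatment group interaction", plus baseline BCVA as a continuous covariate. On covariance, "An unstructured variance-covariance model will be used to account for within-patient correlation", and another structure such as AR(1) is allowed if convergence fails.

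The only size condition is: "Subgroup analyses in population C will be performed only if there are a sufficient number of patients in this population". It gives no number and does not mention Population A. SAP 4.5.2 and 4.5.4 and Protocol 6.6.2 refer to baseline parameters as covariates or in subgroup analysis. None of them adds a treatment-by-subgroup term, an interaction test or a rule for reading subgroup results.

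**The concern.** A subgroup analysis is meant to show whether the treatment effect differs between kinds of patient. Separate models give one difference per level, but neither an estimate of how far those differences are apart nor its uncertainty. The reader is left to compare confidence intervals or p-values across levels, and a comparison of p-values mainly reflects the sample size in each level.

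The second problem is fitting. Each separate model re-estimates the whole covariance matrix and all arm-by-visit means from one level's patients. Where a small level falls back to a simpler covariance and a larger one does not, the results set side by side come from different models. Some levels are also incompatible with the model or population as defined.

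SAP 4.8 calls the study hypothesis-generating, and subgroup contrasts are a natural source of such hypotheses.

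**Working it through.** **Inputs from the documents.** SAP 2.3.1 and Protocol 6.1.1: 68 patients in Arm A and 45 in each of Arms B, C and D, 10% drop-out, SD 13.5, true difference 5.9 letters, one-sided 10%. Completers are 61.2 and 40.5. The schedule has nine post-baseline BCVA visits (Weeks 4 to 36).

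**Assumptions.** The documents give no subgroup shares, so 50:50 is the base case and 90:10 the extreme. They set no subgroup threshold either, so two-sided 0.2 (the primary-endpoint rule) and 0.05 are both shown.

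**Reproducing the plan.** SE = 13.5 × √(1/61.2 + 1/40.5) = 2.73. Power = Φ(5.9/2.735 − 1.2816) = 80.9%, against a stated 80%. Minimum detectable difference = 1.2816 × 2.735 = 3.5 letters, as stated.

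**Same effect in both halves of a 50:50 factor.** SE per half = 2.735 × √2 = 3.87.
- At 0.2: power per half = Φ(5.9/3.867 − 1.2816) = 59.6%. Exactly one half significant: 2 × 0.596 × 0.404 = 48%. Both: 36%. Neither: 16%.
- At 0.05: power per half = Φ(5.9/3.867 − 1.96) = 33.2%. Exactly one: 2 × 0.332 × 0.668 = 44%.

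**Sensitivity: chance that exactly one of two levels is significant, one arm against Arm A.**

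| True effect | Threshold | 50:50 | 70:30 | 90:10 |
|---|---|---|---|---|
| 3.5 letters | 0.2 | 46% | 46% | 48% |
| 3.5 letters | 0.05 | 25% | 25% | 26% |
| 5.9 letters | 0.2 | 48% | 52% | 63% |
| 5.9 letters | 0.05 | 44% | 47% | 53% |
| 8 letters | 0.2 | 34% | 41% | 62% |
| 8 letters | 0.05 | 50% | 55% | 70% |

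In Population C, with SAP 2.3.2 inputs (68 × 0.65 × 0.9 = 39.8 completers per arm, SD 9.7, 4.7 letters), a 50:50 split gives 48% at 0.2 and 44% at 0.05.

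**Size of the within-level models, Population A.** Unstructured covariance over nine visits: 9 × 10/2 = 45 parameters. Means: 4 arms × 9 visits = 36. Completers: (68 + 3 × 45) × 0.9 = 182.7, so a low-luminance-deficit quartile holds about 46 (about 15 in Arm A and 10 in each other arm).

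For the level worse than 20/200, Protocol 4.2.1 gives letters only for 20/40 (69 to 73) and for the 20/320 entry limit (24). Five letters per line would put this level at 24 to 33 letters. The documents give no baseline distribution. A normal baseline truncated to 24–73, with an assumed mean of 48 to 60 and SD of 10 to 15, puts about 1 to 26 of 203 patients there. With complete data, a non-singular nine-visit covariance around four arm means needs roughly 9 + 4 = 13 patients. The quartile clears that, though with little information per parameter. The 20/200 level may or may not.

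**Levels that conflict with the definitions.**
- SAP 4.1.1.3 restricts Population C to BCVA of 68 letters or fewer at Week 12. Its subgroups are also defined at Week 12, and 20/40 starts at 69 letters. The level 20/40 or better therefore has no patients.
- The model contains an indicator for RAP or PCV. Within the PCV and RAP levels it is essentially always present, and within Neither essentially always absent, so its coefficient is not identified.

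**The case against.** The SAP does not say that significance will be compared between subgroups. The rule that a "corresponding unadjusted 2-sided p-value is below 0.2" shows a difference is confined to the primary endpoints at Week 36. The model yields differences with 95% confidence intervals, and because levels are disjoint a reader can form the contrast from them. The SAP is also open about multiplicity ("There will be no formal correction for multiple comparisons"), it has a covariance fallback, and the List of Planned Outputs, which was not available, might add detail. All of this stands and limits the claim. It does not supply the missing estimate: the text specifies no interaction, and a contrast the reader must assemble, possibly from models with different covariance structures, is not a planned analysis.

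Three stronger readings are tempting.
- *A uniform effect will look confined to one subgroup half the time.* This needs a two-level factor, an effect near 5.9 letters and a reader who compares p-values.
- *Small Population A levels cannot be fitted.* The AR(1) fallback makes this a risk, and the count below 20/200 rests on an assumed distribution.
- *Subgroup results will select later trial populations, or will mostly be chance.* No text says the first, and the second is not shown.

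It can also be said that a joint model is no easier, since low-luminance-deficit quartiles give 4 × 9 × 4 = 144 means. Each patient contributes up to nine visits, however, so this is 16 means per visit from about 203 patients, with one covariance matrix estimated from all of them. What remains true is that an arm with no patients in a level is not estimable in either model.

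**Conclusion.** The point holds in this form: the planned subgroup analysis gives no direct assessment of effect differences, and this should be corrected. The 48% and 44% describe what level-by-level reading would produce for a uniform 5.9-letter effect in a 50:50 factor. The figure is 25% to 63% for effects of 3.5 to 5.9 letters, either threshold and splits from 50:50 to 90:10, and an 8-letter effect with a 90:10 split reaches about 70% at 0.05. They are properties of that reading, not error rates of a rule in the SAP.

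On fitting, only one level is shown to be impossible: 20/40 or better in Population C. The RAP-or-PCV covariate is redundant in the ICG-type models, which can be fitted once it is dropped. Small Population A levels are those most likely to need the fallback covariance, so the structure may differ between levels being compared. The study's hypothesis-generating purpose lowers the stakes but does not remove the gap.

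**What to change.** For each factor, fit one MMRM to the whole population with treatment by visit by subgroup terms (and their lower-order terms) and a common covariance matrix. Report the Week 36 difference in each level with its confidence interval, and the Week 36 interaction estimate with confidence interval and p-value, labelled exploratory. State that within-subgroup p-values are not used to conclude an effect or a difference.

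Also:
- set a numeric minimum size per arm and level, applied in Populations A and C;
- remove the level 20/40 or better from Population C;
- omit the RAP-or-PCV covariate from the ICG-type model.

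The cost is SAP wording and a changed model statement, with no new data. The downside is low power for interaction. In a 50:50 split the interaction SE is 3.867 × √2 = 5.47 letters, so power for a 5.9-letter interaction at two-sided 0.2 is about 43%, and 80% power needs (1.2816 + 0.8416) × 5.47 = 11.6 letters. A non-significant interaction must therefore not be read as evidence of a uniform effect, which is why its confidence interval should be shown.

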#### **4.6 SAFETY ANALYSES**

All safety analyses will be based on the safety analysis population. The LoPO contains the full list of reports for safety analyses.

##### **4.6.1 Adverse Events**

The original terms recorded on the eCRF by the Investigators for adverse events will be standardized by the Sponsor. Adverse events will be summarized by mapped term and appropriate thesaurus level, including a separate summaries for ATE events (see [Appendix 3](#)).

Separate summaries will be prepared for systemic and ocular adverse events, with events in the study eye and non-study eye summarized separately. SAEs will be summarized similarly. Adverse events leading to discontinuation from the study will be listed and tabulated.

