2.2 SECONDARY OBJECTIVES

The secondary objectives of this study are as follows:

- To assess the safety of multiple IVT doses of RO6867461
- To assess systemic pharmacokinetics of RO6867461
- To investigate pharmacodynamics and anatomical outcomes informing on the mechanism of action of RO6867461
To investigate the formation of plasma anti-RO6867461 antibodies
- To investigate 2 different RO6867461 dosing regimens

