4.6.6.2 Assessments during Treatment

Under no circumstances will patients who enroll in this study be permitted to be allocated a new randomization number and re-enroll in the study.

On Day 1, baseline assessments will be conducted on the eligible patients, according to the SoA ([Appendix 1](#) and [Appendix 2](#)). Patients will receive their first IVT administration of either RO6867461 or comparator therapy according to the randomization schedule and established standard administration procedures. Patients will return to the eye clinic for study treatment administration (every 4 weeks) and assessments as outlined in the SoA. Patients will be administered the same study treatment throughout the study period, except patients randomized to Arms D and E:

- Patients in Arm D will receive sham administration on Weeks 16, 24, and 32 to maintain the double-masking throughout the Q8W regimen period.
- Patients in Arm E will initially receive 3 injections of ranibizumab followed by 6 injections of RO6867461.

In the study eye, a post-treatment optic nerve head perfusion will be assessed for each patient immediately after study treatment administration (maximum within 15 minutes after treatment administration), by using testing finger count vision, or hand motion or light perception as appropriate.

On the day of dosing, IOP will be monitored at 30 minutes post-treatment administration, and if IOP is ≥ 30 mmHg in the study eye, IOP should be re-assessed at 1 hour post-treatment administration. Patients will be discharged at the discretion of the Investigator.

Patients will be instructed to report any signs or symptoms of intraocular inflammation (uveitis) or endophthalmitis which may be a clinical sign and include symptoms such as pain, photophobia, redness, or reduced vision.

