5.3 METHODS AND TIMING FOR CAPTURING AND ASSESSING SAFETY PARAMETERS

The Investigator is responsible for ensuring that all AEs (see Section 5.1.1 for definition) are recorded on the Adverse Event eCRF and reported to the Sponsor in accordance with instructions provided in this section and in Sections 5.4-5.6.

For each AE recorded on the Adverse Event eCRF, the Investigator will make an assessment of seriousness (see Section 5.1.2 for seriousness criteria), severity (see Section 5.3.3), and causality (see Section 5.3.4).

5.3.1 **Adverse Event Reporting Period**

Investigators will seek information on adverse events at each patient contact. All AEs, whether reported by the patient or noted by study personnel, will be recorded in the patient's medical record. AEs will then be reported on the Adverse Event eCRF as follows:

After informed consent has been obtained **but prior to initiation of study treatment**, only SAEs caused by a protocol-mandated intervention should be reported (e.g., SAEs related to invasive procedures such as angiographies). Any other AE should not be reported.

After initiation of study treatment, all AEs, regardless of relationship to study treatment, will be reported until the final visit.

After a period of 28 days from the last dose of study treatment, Investigators should report any deaths, SAEs, or other AEs of concern that are believed to be related to prior treatment with study treatment (see Section 5.6).

5.3.2 **Eliciting Adverse Event Information**

A consistent methodology of non-directive questioning should be adopted for eliciting AE information at all patient-evaluation time-points. Examples of non-directive questions include the following:

“How have you felt since your last clinic visit?”

“Have you had any new or changed health problems since you were last here?”

5.3.3 **Assessment of Severity of Adverse Events**

Table 3 provides guidance for assessing AE severity.

Table 3 Adverse Event Severity Grading Scale

Severity	Description
Mild	Discomfort noticed, but no disruption of normal daily activity
Moderate	Discomfort sufficient to reduce or affect normal daily activity
Severe	Incapacitating with inability to work or to perform normal daily activity

Note: Regardless of severity, some events may also meet seriousness criteria. Refer to definition of a serious adverse event (see Section 5.1.2).

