## 2. STUDY DESIGN

This is a multiple-center, multiple-dose and regimen, randomized, active comparator controlled, double-masked, five parallel groups, 36-week study in patients with subfoveal CNV secondary to AMD. The study design is shown in Figure 1 Study Design.

The five groups of this study are as follows.

- Arm A: 0.5 mg ranibizumab IVT every 4 weeks for 32 weeks (9 injections)
- Arm B: 1.5 mg RO6867461 IVT every 4 weeks for 32 weeks (9 injections)
- Arm C: 6 mg RO6867461 IVT every 4 weeks for 32 weeks (9 injections)
- Arm D: 6 mg RO6867461 IVT every 4 weeks up to Week 12 (4 injections), followed by 6 mg RO6867461 IVT every 8 weeks (i.e., on Weeks 20 and 28; 2 injections)
- Arm E: 0.5 mg ranibizumab IVT every 4 weeks up to Week 8 (3 injections), followed by 6 mg RO6867461 IVT every 4 weeks (6 injections)

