### **2.3.2 Sample Size and Power for anti-VEGF-Incomplete-Responder Population Evaluation**

The sample size for anti-VEGF–incomplete-responder population is based on the primary efficacy outcome of mean change in BCVA from Week 12 to Week 36 in the subset of anti-VEGF–incomplete-responders, between Arm A and Arm E.

Consider 68 patients randomized to both Arms A and E with 65% meeting the criteria for inclusion in anti-VEGF–incomplete-responder subgroup and a drop-out rate of 10%. Assuming a standard deviation of 9.7 letters, this sample size would provide approximately 80% power to detect a true different of 4.7 letters at the one-sided  $\alpha$  level of 10%. The minimum detectable difference would be approximately 2.7 letters.

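### The SAP text specifies no split of Arm E adverse-event, SAE and ATE summaries at the Week 12 switch, although one third of that arm's scheduled follow-up precedes any RO6867461

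*SAP*

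**What the plan says.** Protocol 4.6.6.2 gives the planned sequence: "Patients in Arm E will initially receive 3 injections of ranibizumab followed by 6 injections of RO6867461". Protocol 5.3.1 sets the collection period: "After initiation of study treatment, all AEs, regardless of relationship to study treatment, will be reported until the final visit". Adverse-event collection in Arm E therefore runs through both drugs.

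For tabulation, SAP 4.6.1 states: "Adverse events will be summarized by mapped term and appropriate thesaurus level, including a separate summaries for ATE events". It goes on to separate systemic from ocular events and study eye from non-study eye, and treats SAEs in the same way. Protocol 6.5.1 makes the same separations. Neither section defines a treatment period or a rule based on treatment at onset.

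Three other SAP sections bear on the grouping:

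- **4.1.2** places each patient in one safety group. Its best-fit rule applies only to patients given a drug other than the one they were randomized to.
- **4.6.8** summarizes exposure by treatment arm and does not separate the two drugs.
- **4.6.5** leaves only Arm A out of the antibody table, so Arm E is kept with the RO6867461 arms.

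SAP 4.6 refers to the LoPO for the complete set of safety reports.

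**The concern.** A secondary objective in Protocol 2.2 is "To assess the safety of multiple IVT doses of RO6867461". Under Protocol 5.7, imbalances of clinical relevance that go against RO6867461 are reported to health authorities. A single Arm E column covering the whole study would mix 12 weeks on ranibizumab with 24 weeks on RO6867461. It would also count patients who stop before Week 12 and never receive RO6867461. SAP 4.1.2 would not move those patients, because they received what they were assigned.

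The arm is large enough to matter. Planned numbers are 45 in each of Arms B, C and D and 68 in Arm E. Arm E is thus 68 of 203 patients due to receive RO6867461 (33%), and 68 of the 158 due to receive 6 mg (45 + 45 + 68; 43%).

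The SAP already recognizes the switch elsewhere: sections 4.1.1.2 and 4.4.2 reset the baseline to Week 12 for the efficacy evaluation of Arms A and E. It states nothing equivalent for adverse events.

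**Working it through.** **Inputs.** The injection counts come from SAP 2, and the reporting period from Protocol 5.3.1 (first dose to Week 36). The arm size and 10% drop-out come from SAP 2.3.2 ("Consider 68 patients randomized to both Arms A and E"). The documents give no adverse-event rates, so the early/late rate ratio is an assumption: 1, with a range of 0.5 to 2.

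**Plan's own figure.** Four-weekly doses at Weeks 0, 4 and 8 make 3. Doses at Weeks 12, 16, 20, 24, 28 and 32 make 6. The total is 9, as the plan states.

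**Share of treatment and time before RO6867461.**

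- Injections: 3/9 = 33.3%.
- Scheduled reporting time: 12/36 = 33.3%, or 816 of 2,448 patient-weeks for 68 patients without drop-out (68 × 12 and 68 × 36).
- With the ±7-day window at Week 12 in Protocol Appendix 1: 11/36 = 30.6% to 13/36 = 36.1%.
- With 10% drop-out at a constant hazard, −ln(0.9)/36 per week: about 15.4 patient-years before the switch and 29.2 after, so 15.4/44.6 = 34.5%.
- If all drop-out fell just before Week 12: 12/(12 + 0.9 × 24) = 35.7%.

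**Share of events.** With early/late rate ratio r and no drop-out, the share is 12r/(12r + 24).

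| r | Share with onset before RO6867461 |
|---|---|
| 0.5 | 6/30 = 20% |
| 1 | 12/36 = 33.3% |
| 2 | 24/48 = 50% |

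**Share of affected patients.** For tables that count patients with at least one event, let p be the proportion affected by Week 36 at a constant rate. The share whose first event precedes Week 12 is [1 − (1 − p)^(1/3)]/p. This gives 34.5% at p = 10%, 41.3% at 50% and 51.9% at 80%.

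**Patients never exposed.** 68 × 0.9^(12/36) = 65.7 remain at Week 12, so about 2 of 68 never receive RO6867461.

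**Dilution against Arm A.** Suppose rates are otherwise constant and RO6867461 multiplies the ranibizumab rate by θ from Week 12. The unsplit Arm E to Arm A rate ratio is (12 × 1 + 24 × θ)/36. For θ = 2 it is 60/36 = 1.67, and for θ = 3 it is 84/36 = 2.33.

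**The case against.** The strongest reply is that the SAP does not say what a reader might infer, namely that adverse events are reported by arm with no split. SAP 4.6.1 names no column grouping. By-arm reporting is an inference from 4.1.2, 4.6.5 and 4.6.8, and the LoPO may list a split table. This stands: the supportable statement is that the SAP text specifies no split.

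Other limits also stand:

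- **Scope.** The gap is confined to AE, SAE and ATE summaries. Laboratory values, antibodies, BCVA and IOP are summarized by visit or time point (SAP 4.6.2, 4.6.5, 4.6.6), which already separates the periods before and after Week 12.
- **Cause.** It is tempting to say that a third of Arm E events come from ranibizumab. Events are recorded whatever their relationship to treatment, so onset before the switch shows timing only. Some will be procedural or background events.
- **Size.** Only the shares of injections and scheduled time are exactly one third. The share of events needs a rate assumption.
- **Reach.** A reader might infer that the whole RO6867461 safety profile is contaminated. No section plans to pool Arm E into an RO6867461 column, and Arms B, C and D (135 planned patients) receive RO6867461 from Day 1. The Arm E column is a valid description of the randomized sequence, and the summaries are descriptive.

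These points narrow the concern but do not remove it. Even if the LoPO lists a split table, the SAP should still state how events are attributed, which denominators apply and how early stoppers are counted.

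**Conclusion.** The concern holds in a limited form. No rule in the SAP text assigns Arm E adverse events, SAEs or ATEs to the period before or after the first RO6867461 injection. A column built from that text would describe the sequence of ranibizumab then RO6867461, and could not be read as the safety of RO6867461.

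Exactly one third of Arm E's scheduled time and injections precede RO6867461. About one third of its events would do so at a constant rate, and 20% to 50% over the assumed range of rate ratios. About 2 of 68 patients would never be exposed, if 10% drop-out is spread evenly. A true doubling after the switch would appear as about 1.67 against Arm A, given otherwise constant rates. The conclusion is subject to the content of the LoPO.

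**What to change.** In SAP 4.6.1, state that:

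1. Arm E AEs, SAEs and ATEs are also tabulated by onset, before versus on or after the first RO6867461 injection, with patient-time denominators for each period.
2. Patients who stop before that injection count only in the pre-switch column.
3. Post-switch Arm E is shown beside Arm A over the same period, starting from Arm A's Week 12 injection. Both arms have the same masked ranibizumab schedule until then, so reaching that visit should not differ by arm except by chance.

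A pooled Arm A and Arm E reference before Week 12 is optional. The whole-study Arm E column can stay, labelled as the treatment sequence. If the LoPO already lists this split, a cross-reference and the counting rule for early stoppers are enough.

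The cost is one flag derived from dosing and onset dates, plus the added table columns. No new data, patients or visits are needed.
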